6 ANALYSIS POPULATIONS

Full Analysis Set: consists of all enrolled subjects who receive at least one dose of investigational product in this study.

7 DATA SCREENING AND ACCEPTANCE

7.1 Handling of Missing and Incomplete Data

Missing clinical outcome data can occur for multiple reasons, including missed subject visits and scales or measures with missing item scores. Missing and incomplete data will be identified by Data Management through a review of tables and listings for this study and investigated for possible resolution prior to the study database lock.

In general, missing data will be treated as missing, unless otherwise specified. When a change from baseline is assessed, only subjects with a baseline and at least one post-baseline measurement will be included in the analysis.

Assessments performed on unscheduled/end of treatment visits can be mapped to scheduled visits (based on target days of the scheduled visits), if the scheduled visits are missing

7.2 Missing Date Imputation Rules

For scheduled visit, the visit number will be used for analyses and the missing date will not be imputed.

Missing Date of the Last Dose of Investigational Product

When the date of the last dose of investigational product is missing for a subject, all efforts should be made to obtain the date from the Investigator. If after all efforts are made it is still missing, the last visit date will be used as the last dose date.

Missing Medical History Related Dates (eg, diagnosis date) or Birth Date

- If only the day is missing, impute the day to first day of the month.
- If day and month are missing, impute to January
- If year is missing, then no imputation will be done, the date will be missing.

If the imputed medical history related date is earlier than birth date, then birth date will be used.

Missing Date Information for Adverse Events and Concomitant Medications

The following conventions will be used to impute missing portions of dates for adverse events and concomitant medications. Note that the imputed values outlined here may not always provide the most conservative date.

Missing Start Dates

• If the day is unknown, then:

- If the month and year match the first dose of investigational product start date month and year in this study, then impute the day of the first dose date.
- Otherwise, assign the first day of the month.
- If the month is unknown, then:
 - If the year matches the year of the first dose of investigational product date in this study, then impute the month and day of the first dose date in this study.
 - o Otherwise, assign 'January'
- If the year is unknown, then the date will not be imputed and will be assigned a missing value.

If the imputed start date is earlier than birth date, then birth date will be used.

Missing Stop Dates

- If the day is unknown, then assign the last day of the month.
- If the month is unknown, then assign 'December.'
- If the year is unknown, then the date will not be imputed and will be assigned a missing value.
- If the resulting end date is after the date of study completion / discontinuation, set the imputed end date as the date of study completion / discontinuation.

Missing Causal Relationship to Investigational Product for Adverse Events

If the causal relationship to the investigational product is missing for an AE that started on or after the date of the first dose of double-blind investigational product, a causality of yes will be assigned. The imputed values for causal relationship to investigational product will be used for the incidence summary; the values will be shown as missing in the data listings.

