#### 7.5.2.10 Adverse Events

For subjects enrolling from an Ultragenyx-sponsored clinical trial, all AEs will be recorded from the time the subject signs the informed consent for this extension study and completion of the End of Treatment visit in the primary study until 30 days after the last dose of study drug. Adverse events reported as ongoing at the primary study's End of Treatment visit and any new AEs prior to Baseline will be reviewed and recorded at Baseline visit. Any enrolling subject who had an early termination in the primary study will have their baseline AE information collected in the same manner as a subject who is treatment naïve or enrolling from a non-Ultragenyx sponsored study (see following paragraph).

For subjects who are treatment naïve or who are enrolling from a non-Ultragenyx sponsored clinical trial, all AEs will be recorded from the time the subject signs the informed consent until 30 days after the last dose of study drug.

The determination, evaluation, reporting, and follow-up of AEs will be performed as outlined in Section 8.5. At each visit subjects will be asked about any new or ongoing AEs since the previous visit. Assessments of AEs will occur at each study visit.

Clinically significant changes from study baseline in physical examination findings, vital signs, and clinical laboratory parameters, will be recorded as AEs or SAEs, if appropriate.

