An AE (classified by preferred term) will be considered a treatment emergent adverse event (TEAE) if it occurred on or after the first dose in this study, and was not present prior to the first dose in this study, or it was present at the first dose in this study but increased in severity during the study.

Subject incidence of TEAEs will be tabulated by SOC and preferred term. Serious adverse events (SAEs), treatment-related TEAEs and treatment-related SAEs will also be summarized.

Detailed listings for all AEs, SAEs, treatment related TEAEs, treatment related SAEs, AEs leading to the discontinuation, and death will also be generated. The severity will be based on Common Terminology Criteria for Adverse Events (CTCAE). If an AE cannot be graded based on CTCAE, the investigator will assign a severity based on 1 = mild, 2 = moderate, 3 = severe, 4 = life threatening, and 5 = Death related to AE.

Patterns of Infusion Associated Reactions (IARs) will be specifically evaluated throughout the study. IARs will be characterized into 4 distinct types based on timing of onset relative to the infusion and specific clinical manifestations: anaphylactoid, anaphylaxis, urticarial (with or without angioedema), and immune complex. Safety reporting of individual AEs will be recorded in parallel. Detailed listings of IARs will be provided.

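### SAP 7.2 can date a pre-dose event to the first CL202 dose, or after its own stop date, because partial start dates are not checked against the stop date or Baseline record

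*SAP*

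**What the plan says.** SAP 7.2 has one set of start-date rules for adverse events and concomitant medications.

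- Day unknown: "If the month and year match the first dose of investigational product start date month and year in this study, then impute the day". The day taken is that of the first dose; in any other month the first of the month is used.
- Month unknown: "If the year matches the year of the first dose of investigational product date in this study, then impute the month and day". Both are taken from the first dose; in any other year January is used. This branch needs only the year to match.
- The one check on an imputed start is: "If the imputed start date is earlier than birth date, then birth date will be used".
- The one check on an imputed stop is: "If the resulting end date is after the date of study completion / discontinuation", in which case it is set back to that date.

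The section adds a caveat: "Note that the imputed values outlined here may not always provide the most conservative date".

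SAP 8.8.1 counts an event as treatment-emergent "if it occurred on or after the first dose in this study, and was not present prior to the first dose in this study". It also counts one that was present at that dose and then became more severe. Protocol 7.6.6.1 describes treatment-emergent events by onset during treatment alone. Under Protocol 7.5.2.10, for subjects coming from a sponsor study, "Adverse events reported as ongoing at the primary study's End of Treatment visit and any new AEs prior to Baseline" are entered at the Baseline visit. The last rule in SAP 7.2 assigns a positive causality when causality is missing and the event started on or after the first dose.

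**The concern.** This database is built to hold events that precede the first CL202 dose: those carried over from the feeder study, those arising before Baseline and, in naïve and IST subjects, those arising between consent and dosing. A rule that moves a partial start date forward to the first dose needs some check that the event had not already begun or ended. SAP 7.2 uses neither the stop date nor the Baseline record for this, and it never compares start with stop.

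Safety is the primary objective, and subject incidence of treatment-emergent events is a main safety table. If prior presence is programmed from the imputed start, an old event enters that table as new. If its causality is also missing, it can enter the related-event table too.

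**Working it through.** The plan states no figure to reproduce, and the point does not depend on a sample size calculation. The check applies the SAP 7.2 rule literally to six hypothetical events, with an **assumed** first CL202 dose on 15 July 2016.

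| Event | Recorded start | True onset | Stop | SAP 7.2 start | Onset on/after dose? | Start under the fix |
|---|---|---|---|---|---|---|
| a | Jul 2016 | 3 Jul 2016 | 8 Jul 2016 | 15 Jul 2016 | yes (wrong) | 1 Jul 2016 |
| b | 2016 | 10 Feb 2016 | 20 Feb 2016 | 15 Jul 2016 | yes (wrong) | 1 Jan 2016 |
| c | 2016 | 10 Feb 2016 | ongoing | 15 Jul 2016 | yes (wrong) | 1 Jan 2016 |
| d | Jun 2016 | 20 Jun 2016 | – | 1 Jun 2016 | no | 1 Jun 2016 |
| e | 2015 | 20 Jun 2015 | – | 1 Jan 2015 | no | 1 Jan 2015 |
| f | Jul 2016 | 20 Jul 2016 | 25 Jul 2016 | 15 Jul 2016 | yes (right) | 15 Jul 2016 |

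**Impossible records.** Event a starts 15 − 8 = 7 days after it ended. Event b also starts after its stop date. Event b tests the logic and is not a likely record, since an event resolved that long before dosing would seldom be collected in CL202.

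**Classification.** Events a, b and c are treatment-emergent if the onset date alone decides. None of them is if "and was not present prior to the first dose in this study" is judged from the stop date (a, b) or from the Baseline record (c). SAP 8.8.1 does not say which data to use.

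**How often the matching branch is wrong.** Assume onset is uniform over the matching period. The share of matching partial dates with true onset before dosing is then (days before the dose) / (days in the period).

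- Day unknown, 31-day month: dose on day 1, 0/31 = 0%; day 15, 14/31 = 45%; day 31, 30/31 = 97%.
- Month unknown, 2016 (366 days): dose on 15 January, 14/366 = 4%; 1 April, 91/366 = 25%; 1 July, 182/366 = 50%; 1 October, 274/366 = 75%; 15 December, 349/366 = 95%.

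These shares illustrate the mechanism and do not predict CL202. For sponsor-study subjects, feeder events that resolved before the End of Treatment visit are not carried over, so uniform onset overstates the pre-dose share.

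**Effect on a table.** SAP 8.8.1 tabulates by subject. One additional misclassified subject adds 1/20 = 5 percentage points to a preferred term at the planned maximum in SAP 3.3, and 1/8 = 12.5 points in the filing analysis of the first 8 rollover subjects in SAP 3.4.

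**Causality.** SAP 7.2 ties missing causality to the start date and has no prior-presence clause. Its anchor is the first dose of double-blind product, which this open-label study does not have. Read as the first CL202 dose, it would assign a positive causality to events a, b and c if theirs were missing.

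**The case against.** The strongest reply is that SAP 8.8.1 already contains the safeguard. A reader might infer from SAP 7.2 that every matching pre-dose event becomes treatment-emergent. For example, with a first dose on 15 October 2015, a carried-over event recorded only as 2015 that began on 1 January moves 287 days. The documents do not support that inference. Such an event is recorded at Baseline, and SAP 8.8.1 excludes it unless it worsened. The displayed date moves; the classification need not.

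Three other inferences also go too far.

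- *Stopped medications become concomitant.* SAP 8.5 requires use between the first and last dose, so a drug with a known earlier stop date does not qualify, whatever start is imputed.
- *Infusion-reaction findings are distorted.* Protocol 7.5.2.11 and SAP 8.8.1 type these reactions by timing relative to the infusion and by clinical manifestations, and nothing says that imputed dates feed that step. For rollover and IST subjects the first CL202 dose is also not the first exposure.
- *Every misdated event adds 5 points.* It does so only if the subject does not already count under that preferred term.

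It is also fair that opportunities are limited. Protocol 7.5.1 holds the CL202 Baseline with the CL301 Week 48 visit, which leaves CL301 subjects little time for a new event to start and resolve before dosing. Adverse events are asked about at every visit, incomplete data are queried before lock, and all events are listed. The error runs toward over-counting, and the SAP admits that its dates are imperfect.

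What remains is that the safeguard has no named data source, the protocol definition lacks it, and the causality rule does not use it. A general caveat about conservatism does not justify a start date after a known stop date.

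**Conclusion.** The point holds in limited form. As written, SAP 7.2 can place a start date after the event's own stop date, or date a documented pre-existing event to CL202 Day 1. Misclassification as treatment-emergent is possible but not automatic. It requires either that prior presence in SAP 8.8.1 be derived from the imputed start, or that the onset-only definition in the protocol be applied. Counting as related further requires missing causality and the reading of the causality rule given above.

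Complete dates, and partial dates in a non-matching month or year, are unaffected. The direction is over-counting. The total effect cannot be calculated, because the number of partial dates is not given; the 5 and 12.5 point figures are per additional misclassified subject. This is a minor defect, worth correcting because the correction is cheap.

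**What to change.** In SAP 7.2, impute the first-dose date only if both conditions hold: the stop date is missing or falls on or after the first dose, and the event or medication was not recorded at Baseline as ongoing or past. Otherwise impute the earliest date that the known parts allow, never later than the stop date. In the six test events this moves a, b and c before the dose and leaves the true on-treatment event f treatment-emergent.

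In SAP 8.8.1, state that presence before the first dose is decided from the Baseline adverse event record and the stop date, not from the imputed start date. This second change is needed as well: if the first dose falls on the first of the month, the earliest possible start for an unknown day is the dose date itself, and the date alone cannot separate the cases.

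The cost is about two SAP sentences and a small change to the derivation code, with no new data collection.

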# 7 INVESTIGATIONAL PLAN

#### 7.1 Overall Study Design and Plan

This is a multi-center, multinational, open-label treatment and extension study in subjects with MPS 7. The study will assess long-term safety and efficacy of UX003 treatment and will continue for approximately 144 weeks or until one of the following occurs: the subject withdraws consent and discontinues from the study, the subject is discontinued from the study at the discretion of the Investigator or Ultragenyx, or the study is terminated.

Subjects with MPS 7 who are UX003 treatment-naïve or previously enrolled and treated in a prior clinical study of UX003 may have the option to enroll into this treatment and extension study provided all eligibility criteria have been met for a given subject. Subjects with MPS 7 who were enrolled in either an Ultragenyx sponsored study (e.g., UX003-CL301) or non-Ultragenyx sponsored clinical studies (e.g., ISTs, expanded access/compassionate use) may be eligible for enrollment. Those subjects enrolling from a previous UX003 study should have a reasonable benefit-risk assessment from their primary study as determined by the Investigator, in order to continue with long-term therapy in this extension study. To be enrolled, subjects need to meet all inclusion/exclusion criteria.

All subjects will receive 4 mg/kg UX003 QOW unless data from prior studies define a different dose either for that subject or the use of UX003 in general.

As has been observed with other MPS ERTs, some subjects may experience infusion-associated reactions (IARs) with the administration of UX003. Thus, prophylactic antihistamine will be administered prior to each study drug infusion. Antipyretic pretreatment may also be given at the Investigator's discretion. To minimize the potential for IARs, infusions will initially be administered on a slower rate schedule followed by an increase in rate. Infusion rate may be slowed to manage or reduce IARs.

Safety will be monitored throughout the study based on physical examinations, clinical laboratory analyses, and reporting of adverse events (AEs) and SAEs.

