3.6 Randomization and Blinding

All subjects received UX003 on an open-label basis. Randomization, blinding and stratification factors are not needed for this study design.

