8 STATISTICAL METHODS OF ANALYSIS

8.1 General Principles

All analysis will be performed based on full analysis set, and summaries will be presented overall and for naïve, IST and rollover subjects separately. The statistical analyses will be reported using summary tables, figures, and data listings. Statistical tests will be 2-sided at the alpha =0.05 significance level. All p-values will be presented as nominal p-values. Continuous variables will be summarized with means, standard deviations, medians, minimums, and maximums. Categorical variables will be summarized by counts and by percentages of subjects in corresponding categories. All raw data obtained from the CRFs as well as any derived data will be included in data listings.

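### SAP 7.2 ties its missing-causality rule for AEs to a double-blind first dose that this open-label study does not have, so as written the rule never applies

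*SAP*

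**What the plan says.** SAP 7.2, under its sub-heading on missing causal relationship, covers an AE whose relationship to study drug was not recorded. If the event started "on or after the date of the first dose of double-blind investigational product, a causality of yes will be assigned". The section then says where this is used: "The imputed values for causal relationship to investigational product will be used for the incidence summary". The listings continue to show causality as missing.

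On design, SAP 3.6 states "All subjects received UX003 on an open-label basis" and adds "Randomization, blinding and stratification factors are not needed for this study design". Protocol 7.1 agrees: "This is a multi-center, multinational, open-label treatment and extension study in subjects with MPS 7".

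SAP 7.1 sets the default where no specific rule applies: "In general, missing data will be treated as missing, unless otherwise specified".

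SAP 8.8.1 lists the outputs that depend on causality: "treatment-related TEAEs and treatment-related SAEs will also be summarized".

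**The concern.** The rule depends on a date that does not exist in this study. No subject receives a double-blind dose in CL202, so no AE can start on or after one. A provision meant to err towards calling an event related therefore does nothing when applied as written. An event with unresolved causality is then not counted among the related events.

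Long-term safety is the primary objective, and Protocol 7.6.6.1 requires AEs to be summarised by relationship to study drug. The affected tables are therefore central outputs. The error can only lower the related counts, which favours the product. The outcome also depends on how a programmer chooses to read a phrase that has no referent here, and the SAP should settle that beforehand.

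**Working it through.** The plan states no figure to reproduce. The check compares the texts and then works out what one affected subject would change.

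**1. Anchors used for AEs in the SAP**

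| Rule | Place | Anchor |
|---|---|---|
| Imputing partial AE start dates | SAP 7.2 | First dose of investigational product in this study |
| Treatment-emergent status | SAP 8.8.1 | First dose in this study |
| Imputing missing causality | SAP 7.2 | First dose of double-blind investigational product |

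Only the causality rule departs from the anchor of this study's first dose. It is also the only one whose anchor conflicts with SAP 3.6 and Protocol 7.1.

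**2. Literal reading**

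- Condition: AE onset on or after the first double-blind dose.
- Double-blind doses in CL202: none.
- The condition is therefore never true and nothing is imputed.
- SAP 7.1 then leaves causality missing. That section opens on clinical outcome data, but its default is worded generally and no other rule covers causality.
- An event with missing causality does not enter the treatment-related TEAE or SAE counts.

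**3. Purposive reading**

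If the phrase is taken to mean the first dose in this study, every TEAE that began on or after that dose and has missing causality is imputed as related. The under-count is zero.

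**4. Size under the literal reading**

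A subject changes the incidence only if the event with missing causality is that subject's sole candidate related event. The shift per such subject is 1/N.

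- N = 20 (SAP 3.3, up to 20; Protocol 7.6.1, approximately 20): 1/20 = 5.0 percentage points.
- n = 8 (SAP 3.4, analysis for filing once the first 8 rollover subjects reach Week 12, assuming those 8 form the denominator): 1/8 = 12.5 percentage points.

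The documents give no number of affected subjects. For an assumed range of 0 to 2:

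- N = 20: 0 to 2/20 = 0 to 10 points.
- n = 8: 0 to 2/8 = 0 to 25 points.

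**The case against.** The strongest reply is that this is a wording slip with little or no effect. The purpose of the rule is plain, the date rules in the same section use this study's first dose, and a sensible programmer would do the same. Missing causality should also be rare. Protocol 8.5.4.1 makes relationship to study drug a required AE detail, Protocol 8.4.2 has missing data resolved with the investigator, and SAP 7.1 has missing data investigated before database lock. Any remaining case would be visible as missing in the listings, which are easy to check with about 20 subjects. Overall TEAE and SAE incidence does not use causality and is unaffected.

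All of this stands, and it limits the point to a possible and probably small under-count. It does not make the text right: the rule is operative, and its condition conflicts with the design. The filing analysis also comes at Week 12 of the first 8 rollovers, whereas resolution of missing data is tied to database lock, so more causality fields could be open at that stage. That last step is an inference.

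A reader might infer more, in three ways that the documents do not support:

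- *That rollover TEAEs would be under-counted if the phrase meant a feeder-study dose.* A feeder-study dose precedes the first dose here. Every rollover TEAE would therefore satisfy the condition and be imputed as related.
- *That the rule would create a difference between the groups which SAP 8.1 reports separately ("summaries will be presented overall and for naïve, IST and rollover subjects separately").* This needs a double-blind feeder study. The documents mention a randomization visit in UX003-CL301 but do not say that the study was double-blind.
- *That the shift within a small naïve or IST group would be much larger.* The documents give no sizes for these groups, so any such figure would rest on an invented denominator.

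**Conclusion.** The point holds as an error in an operative rule. As written, the trigger for imputing missing causality as related cannot be met in CL202, and the SAP's own default then leaves those events out of the treatment-related summaries. The contradiction is certain from the text. The under-count is conditional: it requires that the rule is programmed literally, that some causality fields remain missing at analysis, and that the subjects concerned have no other related event. Where all three hold, the related-AE incidence falls by 5 points per subject at N = 20, or 12.5 points at n = 8. Where the phrase is read as this study's first dose, nothing changes. The safeguards on data collection suggest few affected events, but no rate is given. The correction is worth making because it concerns a primary-objective output and costs almost nothing.

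**What to change.** In the missing-causality paragraph of SAP 7.2, replace the reference to the first double-blind dose with *the first dose of investigational product in this study*, and state that it applies to naïve, IST and rollover subjects. This matches the AE start-date rules in SAP 7.2 and the TEAE definition in SAP 8.8.1. Keep the rest of the rule: imputed as related in the incidence summaries, shown as missing in the listings. If programs for the filing analysis already exist, check which reading they implement.

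The cost is one phrase in a SAP revision, with no change to data collection or method. The related-AE figure may become slightly less favourable.
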